## 5.5 Outcomes:

5.5.1 *Feasibility*: The feasibility objectives for this pilot study are to:

1. verify recruitment, consent and randomisation procedures;
2. confirm the sample size required for a fully study;
3. confirm the inclusion/exclusion process;
4. test the appropriateness of assessment tools used in the study;
5. determine appropriate timing of data collection;
6. confirm that the data collection materials are sufficient;
7. monitor the operational processes; and
8. formalize the protocols for Nordic pole walking exercise prescription.

See the chart in ATTACHMENT 9 for further explanations and a more detailed list of feasibility measurements. Notes regarding the study process will be documented throughout the study. Participants upon study completion will also complete a program evaluation survey (ATTACHMENT 10) to reflect on their experience.

5.5.2 *Participant Characteristics*: Participant demographics (ATTACHMENT 11), general health history, smoking status, physical activity level (ATTACHMENT 12)(39), height, weight, girth measurements (bicep, chest, waist, hips and thigh), resting heart rate and oxygen saturation levels (ATTACHMENT 13) will be recorded to provide further understanding of the composition of the participant group.

5.5.3 *Physical Function*:

- 1) *Lower body physical function* will be measured using the 6MWT(40) and the 30-second (30-s) chair stand test(41). The 6MWT has been recognized by the American Thoracic Society as a valid measure of submaximal functional capacity in those with pulmonary disease(40). This self-paced test measures the distance that an individual can walk over a 25 or 30m track in six minutes(40). Granger et al. estimated the minimal important difference for

deterioration of the 6MWT in lung cancer to be between 22m and 42m or a change of 9.5%(42). Having a greater 6MWT distance was correlated with better function, increased physical activity and decreased dyspnea(42). The 30-s chair stand test is a valid indication of lower body strength in the older adult population(41). The test requires participants to complete as many sit to stands as possible in 30 seconds(41). The 30-s chair stand test has been used to assess lower body strength in pulmonary fibrosis patients(43) and the COPD population(44).

- 2) *Upper body physical function* will be assessed with the unsupported upper limb exercise test (UULEX)(45, 46) and the handgrip strength test. The UULEX is a valid incremental test that has been used to measure peak unsupported arm exercise capacity in the chronic lung disease population (45, 46). The test requires the seated participant to lift a plastic bar (0.2kg) through eight levels at a constant cadence of 30 beats per minute as directed by a metronome. Once the maximum height is reached the weight of the bar is increased by 0.5kg every minute to a maximum weight of 2.0 kg. The test continues until the participant experiences fatigue and decides to stop. The results are recorded in seconds. Handgrip strength is correlated with survival, weight loss, sarcopenia and quality of life characteristics in advanced cancer patients(47, 48). As recommended by the American Society of Hand Therapists grip strength will be measured using a dynamometer with the handle in the second position. Individuals will be seated with their shoulder adducted and elbow flexed 90° and their forearm in neutral. Three successive trials for both hands will be recorded.

5.5.4 *HRQoL*: HRQoL has been shown to be a significant independent predictor of survival duration in the cancer population(49). We will assess HRQoL in NSCLC patients using the SF-36 (ATTACHMENT 14)(50) and the Functional Assessment of Cancer Therapy – Lung (FACT-L) (version 3) (ATTACHMENT 15)(51).

The SF-36 has been validated and used extensively as a measure of HRQoL(50). It assesses eight health concepts: 1) Limitations in physical activities because of health problems; 2) Limitations in social activities because of health problems; 3) Limitations in usual role activities because of health problems; 4) bodily pain; 5) general mental health (psychological distress and well-being); 6) limitations in usual role activity because of emotional problems; 7) vitality (energy and fatigue); 8) general health perceptions. The SF-36 has been used in other studies to examine HRQoL in the NSCLC population(52-55).

The FACT-L is a 44-item self-report instrument that measures quality of life using the following dimensions: physical well-being, emotional well-being, social well-being, functional well-being and disease specific concerns(51). The questionnaire begins with the FACT- General (FACT-G); a HRQoL questionnaire that was developed to be used with patients who have any form of cancer(51). It is supplemented with the Lung Cancer Subscale (LCS), which was designed to complement the FACT-G by obtaining related information about the symptom experience of people with lung cancer(51). The FACT-L has been proven to be reliable, valid, and sensitive to change in performance status(51).

## **6.0 Study Procedures** (For a detailed flow diagram of study procedures see ATTACHMENT 16.)

6.1.1 Randomization: Randomization of intervention and control groups will be computer generated(56) and administered by the research development assistant at the university, [name]. [name] will be kept at arm's length from the study to mitigate the risk of bias for the random allocation. Allocation will be concealed by placing the assignment within aluminum foil, and then in opaque envelopes. Study participants will choose and open the allocation envelope.

6.1.2 Assessment: Written consent (ATTACHMENT 5) will be obtained from all participants prior to

their enrolment in the study. All participants will be scheduled for an initial assessment (approximately 1.5 hours in length) that will begin with a brief interview to complete the demographics questionnaire (ATTACHMENT 11) and the short form International Physical Activity Questionnaire (ATTACHMENT 12)(57). They will then have their height, weight, circumference measurements (biceps, chest, waist, hips, thigh), resting heart rate, and oxygen saturation levels measured (ATTACHMENT 13). Following these measurements participants will complete the lower and upper body physical function assessments (ATTACHMENT 13). Finally participants will be given the option of completing the HRQoL questionnaires (ATTACHMENTS 14 & 15) on site or take them home for completion over the phone.. The questionnaires take approximately 25 to 35 minutes in total to complete. Researchers will document and describe any planned exercise that participants are taking part in. After the eight-week time period all participants will be scheduled for a follow-up assessment that will include all of the baseline measures (ATTACHMENT 17). Participants will also be asked to complete the program evaluation survey (ATTACHMENT 10) that will assist researchers in assessing the feasibility of the study. Both assessment sessions will be supervised by the primary investigator, [name], a Registered Kinesiologist. If the participant indicates any distress, they will be offered the opportunity to skip questions or withdraw and receive no further contact from the research team. If necessary the research team will advise the participant to seek a referral to a mental health professional from their own healthcare providers (e.g. family physician).

6.1.3 Intervention: The intervention group will participate in an eight-week NPW program. It will consist of one supervised group NPW session per week (approximately 1 hour in length) and three independent NPW sessions per week. Participants will be instructed on using the poles either immediately after their initial assessment or on an alternate date that is agreed upon (ATTACHMENT 18). They will be asked to practice for one week using the poles prior to their first group session to account for learning effect. Participants will then be assigned to a specific NPW prescription group (Group 1 - compromised (ATTACHMENT 19), Group 2 - inactive (ATTACHMENT 20) or Group 3 - minimally active and highly active (ATTACHMENT 21)) based on their IPAQ score and the observed ability level during the individual instruction session. Participants will be asked to follow their specific individualized NPW prescription throughout the study. During the group sessions the research team who have been trained in instructing NPW will correct technique, ensure participants are progressing according to the pre-determined exercise prescription and address any questions or concerns. Participants will receive training in exercise to mitigate minor risks and help assure their safety. Also participants will be instructed to closely monitor themselves and to maintain exertion to levels that suit their physical capacity (well below exhaustion). After consent is obtained each participant will be asked to provide the name and contact information of someone that they would like to be contacted should an emergency medical situation occur during their participation in the study. This information will be kept in a secure location separate from the data collection sheets during the assessments and Nordic pole walking sessions. Participants will be told to immediately report any exercise related symptoms to the research team. If there are adverse effects that can't be managed in collaboration with the participant and the on-site researchers, the Emergency Medical System will be initiated and the emergency contact that they have provided will be contacted. Additional supports may be utilized by participants (such as oxygen, tables, walls and chairs). Participants will be provided with the principal investigator's contact information should they have any questions or concerns about completing the Nordic pole walking sessions independently. Participants will be asked, but not compelled to engage in these unsupervised sessions.

To promote program adherence participants will be asked to set exercise related goals

(ATTACHMENT 22) prior to beginning the NPW program. Documentation of program adherence is critical to understanding treatment dose(58). Therefore each time participants complete a NPW session (supervised or at home) they will be asked to make an entry in a journal (ATTACHMENT 23) reporting distance walked, duration, and rate of perceived exertion. On days when participants do not complete a NPW session they will be asked record the reason they were not able to walk. The research team will contact participants over phone on a weekly basis to encourage participation as well as answer any questions or concerns that arise (ATTACHMENT 24). At the end of the program participants will reflect back on the goals they set to see how close they have come to achieving them.

The control group will be instructed to continue their usual daily routine for eight-weeks and will be invited to participate in the same NPW program after this time period.

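### The SF-36 and FACT-L come after the physical tests, on site or at home by phone as the participant chooses, so HRQoL answers can vary with time since exertion, place and mode

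*Combined protocol and SAP*

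**What the plan says.** Section 6.1.2 (Assessment) sets the order of the initial visit: an interview, body measurements, then "Following these measurements participants will complete the lower and upper body physical function assessments", and last the quality-of-life forms: "Finally participants will be given the option of completing the HRQoL questionnaires (ATTACHMENTS 14 & 15) on site or take them home". The full option reads "on site or take them home for completion over the phone", so the home route also changes the mode to telephone. The follow-up visit after eight weeks repeats the baseline measures.

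Section 5.5.3 names the physical tests: the 6MWT, the 30-second chair stand, the UULEX and three handgrip trials for each hand. Of the UULEX it says: "The test continues until the participant experiences fatigue and decides to stop".

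Section 5.5.4 describes the content of the forms. The SF-36 covers bodily pain among its eight concepts, and the list ends with "7) vitality (energy and fatigue); 8) general health perceptions". The FACT-L covers physical well-being and has a lung cancer symptom subscale.

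Section 6.1.3 allows pole instruction directly after the initial assessment or on another agreed date, followed by a week of practice. Section 7.0 plans a signed-rank test for change over time and a Mann-Whitney test between groups, with nothing on where or how the forms were completed.

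**The concern.** Some participants will rate energy, pain and symptoms shortly after physical testing, in person. Others will do so later, at home and by telephone. Time since exertion, place and mode all change together, and the participant decides. The same person may answer under different conditions at baseline and week 8.

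HRQoL is one of two secondary objectives and has its own hypothesis (section 4.0). Varying conditions add noise to a sample of about 10 per arm. They turn into bias if the choice of setting differs by arm at week 8, or shifts between visits within an arm. Because the supplied text does not ask for setting to be recorded, neither could be examined afterwards.

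One route is specific to the intervention arm. With no window on home completion, an intervention participant who takes the baseline forms home could answer after pole instruction has begun. A control could not.

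The pilot also aims to confirm the full-study sample size, test the assessment tools and settle the timing of data collection (section 5.5.1, objectives 2, 4 and 5). Avoidable variation in HRQoL weakens all three.

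**Working it through.** The plan states no effect size, SD or power, so there is no figure of its own to reproduce. The documents give the visit order, the on-site or home-by-phone option, 10 per arm (section 5.4), a visit of about 90 minutes, 25 to 35 minutes for the questionnaires, and the two tests in section 7.0. Everything else below is assumed, for scale only.

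**1. Shift in the between-arm contrast.** Bias = effect of answering on site (s, in SD) × difference between arms in the share answering on site. With a difference of 0.3 (3 of 10):
- s = 0.2: 0.2 × 0.3 = 0.06 SD
- s = 0.5: 0.5 × 0.3 = 0.15 SD
- s = 0.8: 0.8 × 0.3 = 0.24 SD

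The standard error of a difference in means is √(1/10 + 1/10) = 0.45 SD. The shifts are therefore about 0.13, 0.34 and 0.54 standard errors.

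**2. Could a gap of 3 in 10 arise by chance?** If every participant is equally likely to choose either setting, the exact binomial calculation gives the probability that the arms differ by:
- at least 2 on-site completers: 50%
- at least 3: 26%
- at least 4: 12%

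**3. Added noise in change scores.** Take a baseline to week 8 correlation of 0.6 and an independent 50/50 choice at each visit. The variance of change without a setting effect is 2 × (1 − 0.6) = 0.8. Setting adds s² × (0.25 + 0.25) = 0.5s²:
- s = 0.2: 0.02, or 2.5% of 0.8
- s = 0.5: 0.125, or 16%
- s = 0.8: 0.32, or 40%

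A full-study sample size based on that variance grows in the same proportion.

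**4. False positives.** These come from simulations with no true treatment effect, 10 per arm, 4000 runs per scenario, correlation 0.6, baseline choice 50/50, on-site answers lowered by s, and Mann-Whitney applied to change scores (section 7.0 does not say whether change or follow-up values are compared).
- Equal week 8 choice in both arms, s = 0.5: about 4%.
- On-site share at week 8 of 20% in the intervention arm and 80% in control: about 9% (s = 0.5) and 15% (s = 0.8). The signed-rank test within the intervention arm then rejects in about 7.5% and 10%.

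Equal choice by arm leaves the between-arm error rate intact. A marked inflation needs both a large split and a sizeable s.

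**5. Visit time.** If the 90 minutes include on-site completion, 90 − 35 = 55 to 90 − 25 = 65 minutes remain for the rest. Moving the forms forward does not change that total.

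**The case against.** Much can be said for the plan. The 6MWT is described as self-paced and submaximal, the chair stand lasts 30 seconds, and only the UULEX, a seated arm test, runs to fatigue. Section 6.1.2 gives neither the order within the battery nor the interval before the forms, so answering immediately after exhausting tests is an inference. The attachments with the flow diagram, visit sheets and questionnaires are not in the supplied text and may set a rest or a recall period. Breathlessness is not named as an item of either form. All of this stands, and it limits the claim to answers that *can* vary.

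The option is also written only for the initial visit. That does not help. If it carries over to week 8, the setting can change by choice. If week 8 is always on site, everyone who answered baseline at home changes setting.

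A reader might infer three stronger points that the documents do not support:
- **Test results colour the answers.** No section says participants are shown their results.
- **The artefact could account for most of the expected HRQoL effect.** The review cited in section 3.3 gives an SMD of 0.17, but its 95% CI runs from -0.16 to 0.49. It is reported as no difference and comes from patients after resection, not a stage I-IV sample. It is no yardstick for an assumed shift.
- **The bias favours the walking program.** If walkers stay on site and answer tired while controls answer rested, a benefit would be masked. The reverse pattern would exaggerate one.

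Lastly, this is a feasibility pilot, and timing of data collection is among the things it studies. That supports recording the setting. A pilot that neither fixes nor records it learns little about timing.

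**Conclusion.** The concern holds as a weakness in a stated procedure. The forms follow the physical tests, and participants choose between two settings that differ in time since exertion, place and mode. Nothing supplied keeps the setting constant or records it.

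The certain consequence is uncontrolled variation in how a secondary outcome is collected. Bias is conditional on the choice differing by arm or changing between visits, and its direction is unknown. On the assumed values the between-arm shift is 0.06 to 0.24 SD, within sampling error for this pilot. The case for change therefore rests on how cheaply the variation can be avoided, on its not being repairable after data collection, and on its carrying over into the full-study design. The importance is moderate. The conclusion rests on the supplied text, since the attachments could contain a rest interval or a record of setting.

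**What to change.** In section 6.1.2, have participants complete the SF-36 and FACT-L on site, after written consent and before any physical test, at both visits.

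Where home or phone completion is still needed:
- use the same place and mode at baseline and week 8;
- complete the baseline forms before any pole instruction;
- record place, mode and date of completion for every participant at both visits.

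Baseline forms should not be sent out ahead of the visit in general. On the clinic and poster recruitment routes, section 5.4 places written consent at the first face-to-face visit, so forms completed earlier would precede it.

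The cost is a re-ordered visit sheet and a few recorded fields, with no new instrument. Participants sit for about 30 minutes before the physical tests and have less choice. Those who would have taken the forms home spend 25 to 35 minutes longer on site.

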## **7.0 Statistical Analysis**

Narrative descriptions will be used to address feasibility outcomes. Descriptive statistics (mean, median, standard deviation) will be calculated for any numeric data. Non-parametric tests will be used to compare the intervention and control group due to small sample size; a Wilcoxon signed-rank test to see if changes occurred over time and a Mann-Whitney U test to see if there was difference between groups. A p-value of less than 0.05 will considered significant.

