In 2013 Cheville et al. in a RCT (n=66) examined the effects of a home-based walking and strength training exercise program (versus usual care) on function, fatigue and sleep quality in patients with stage IV lung and colorectal cancer(24). Twenty out of 26 of the participants in the intervention group adhered to the program. They showed improvement in mobility (p=0.01), fatigue (p=0.02) and sleep quality (p=0.05) over time. The mean changes (from baseline to week eight) between the intervention and control groups in mobility (p=0.002), fatigue (p=0.03), and sleep quality (p=0.002) also significantly differed. (24). Henke et al. (2014) also conducted a RCT (n=46) to test the effects of strength and endurance training on the independence and quality of life in lung cancer patients with advanced disease during three cycles of palliative chemotherapy treatment(25). The intervention group (n=18) participated in cardiovascular exercise daily and strength training every other day(25); the control group (n=11) received conventional physiotherapy consisting of manual therapy and breathing techniques(25). Out of 46 patients only 29 completed the trial; 17 patients ended the trial early due to death (n=6), non-compliance (n=10) or because they continued treatment at a different hospital (n=1)(25). A significant difference between groups was found in physical function, self-reported symptoms (pain, neuropathy, cognitive functioning, dyspnea) and exercise capacity(25).

This evidence suggests that exercise capacity and symptom burden in patients with advanced lung cancer can be improved with exercise, however frequency, duration and intensity of prescription are not certain. Most studies on exercise in this population have consisted of in-hospital supervised exercise programs, which may be restrictive to some patients and has been associated with poor compliance. There is a need to further examine home-based exercise programs including new modalities of exercise that may not have been accessible in the clinical setting(26).

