takes for participants to complete questionnaires. iii) *Management*: To observe any potential human and data optimization problems that may occur(37). For example, issues that may arise at participating centres. iv) *Scientific*: To assess treatment safety, determine dose levels and response and estimate treatment effect and its variance(37). While pilot studies have little to contribute statistically and theoretically, they provide extensive understanding of the research process(38). Therefore, researchers need to remain open-minded, using the results of the pilot study to adapt the design and operational processes of a full study(38).

- 3.6 Knowledge Gaps and Contribution to Research: There is a growing body of evidence supporting exercise in the NSCLC population and health care professionals are encouraged to recommend that NSCLC patients participate in an exercise program. However, there is a need to establish the most appropriate and effective exercise prescription for this population. Currently, there is insufficient evidence regarding the optimal exercise type and prescription for the NSCLC population(12). To assist health care professionals with making exercise recommendations for this population more rigorous, methodological studies (i.e. RCTs) examining the effects of various exercise types and prescriptions, such as resistance training and Nordic pole walking are needed. To accomplish this a feasibility or pilot study is required to establish the optimal study design, population, assessment tools, interventions and operational processes. It has been recognized that poor accessibility to rehabilitation programs for lung cancer patients is a barrier to exercise program participation (ref Didier). Therefore future studies should consider home-based programs particularly for those with advanced disease.

NPW has been selected as an appropriate exercise for NSCLC patients because of its ability to be a more intense and beneficial exercise compared to regular walking(27). It also allows patients to exercise independently. A study of individual/group exercise using NPW will be the first of its kind and is the first step to establishing the appropriate NPW exercise prescription including the optimal frequency, intensity and time spent NPW for individuals with NSCLC.

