#### 4.0 Research Objectives, Questions & Hypotheses

The *primary research question* is: 1) What is the optimal design (patient sample, instruments) and operational processes to assess the effects of NPW on individuals who have been diagnosed with stage I-IV NSCLC? *Secondary research questions* are: 2) How does participating in an eight-week Nordic pole walking program affect physical function, and 3) health related quality of life (HRQoL) of these individuals?

The *primary objective* is to assess the feasibility of a NPW program for individuals with stage I-IV NSCLC by establishing the optimal design and operational processes. The *secondary objectives* are to: determine the effects of NPW on 1) physical function, and 2) HRQoL.

*Hypotheses* are that the NPW program for individuals who have been diagnosed with stage I-IV NSCLC will: 1) be feasible; 2) improve physical function; and 3) improve the HRQoL.

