#### 5.0 Methods:

- 5.1 Study Design: This is an eight-week multi-centre randomized controlled pilot study to establish optimal study design and operational processes to inform a larger scale study(37, 38). The intervention group will participate in an individualized NPW program, while the control group continues their usual daily routine. The control group is necessary because it increases the reliability of the results by allowing researchers to compare the control group measurements to the intervention group measurements.

- 5.2 Location of Research:

1. Lakeridge Health, Oshawa, Ontario (n=5 intervention, n=5 control, approximate eligible population at Lakeridge is 300, this is based on current and new cases of lung cancer at the Durham Regional Cancer Centre)
2. Southlake Regional Health Centre, Newmarket, Ontario (n=5 intervention, n=5 control)
3. Abilities Centre, Whitby, Ontario (ATTACHMENT 1)
4. Magna Centre, Newmarket, Ontario (ATTACHMENT 2)

5.3 Sample Selection: The *inclusion criteria*: 1) primary diagnosis of histologically confirmed stage I-IV NSCLC (with any concurrent cancer treatment), 2) approval of primary treating physician, and 3)  $\geq 18$  years old. The *exclusion criteria*: 1) not able to communicate in English, 2) unable to consent, e.g. incapable, and 3) use of Nordic walking poles on a regular basis within the last six months. We will presume the study participant is capable with respect to the research study unless we suspect incapacity exists based on: the physician's assessment; direct observation of the person e.g., the person is confused, disoriented, depressed, psychotic, extremely anxious, unable to make a decision, intoxicated; or from information obtained from family or other caregivers.

5.4 Recruitment: We anticipate recruiting a minimum of 20 individuals with NSCLC (n=10 intervention group, n=10 control group). It is important that the pilot study be representative of the target study population(37, 38). The sample size needs to be large enough to provide useful information about the feasibility of the study(37, 38). Recruitment and enrolment will take place from approximately November 2015 – April 2016. The recruitment procedures are as follows:

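### Section 7.0 does not name the variable for the between-arm Mann-Whitney test and plans no between-arm difference or confidence interval; its pre-post signed-rank test does not compare the arms

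*Combined protocol and SAP*

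**What the plan says.** Section 7.0 is the whole analysis plan in the supplied text. It opens the tests with "Non-parametric tests will be used to compare the intervention and control group due to small sample size" and then names them: "a Wilcoxon signed-rank test to see if changes occurred over time and a Mann-Whitney U test to see if there was difference between groups". Significance is set at p<0.05. The planned summaries are given as "Descriptive statistics (mean, median, standard deviation) will be calculated for any numeric data", which I take to mean per arm. Feasibility outcomes are to be described in narrative.

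Other sections bear on the choice:
- Section 4.0 sets the secondary objectives, to "determine the effects of NPW on 1) physical function, and 2) HRQoL".
- Section 5.1 explains the control group as a means to "compare the control group measurements to the intervention group measurements".
- Section 5.5.1, objective 2, is to confirm the sample size of the full study.
- Section 6.1.2 repeats all baseline measures after eight weeks in both arms.
- Section 3.5 lists, among the general reasons for a pilot, to "estimate treatment effect and its variance".

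**The concern.** Three things are left open or loosely placed.

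1. The variable for the Mann-Whitney test is not named. If week-8 values are used, the baseline measurements play no part in the comparison of arms. If change is used, they do. Both analyses are possible with the data collected, so the choice could be made after results are seen.

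2. No between-arm difference or interval is planned. With about 10 per arm, a p-value alone hides how imprecise the comparison is, and a reader planning the full study gets no effect estimate with its uncertainty.

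3. The signed-rank test of change over time stands in a sentence about comparing the two groups. A paired pre-post test, per arm or pooled (the plan does not say which), does not compare arms. If both arms improve for reasons unrelated to walking, it can be significant with no programme effect. If untreated patients decline, as Section 2.0 describes, and walkers hold steady, it can miss a benefit.

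**Working it through.** **Inputs from the documents.** Section 5.2 gives 5 + 5 participants at each of two hospitals: 2 × (5 + 5) = 20, or 10 per arm, which agrees with Section 5.4. Section 5.5.3 cites a minimal important difference of 22 to 42 m for worsening on the 6MWT. The documents give no power, target effect, SD or dropout rate behind the 20, and no baseline-to-follow-up correlation (rho).

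**Assumptions.** Two-sided 5% level; 10 per arm with complete data; equal SD at both visits; effect 0.5 SD; rho from 0.3 to 0.9; three distributions (normal, heavy-tailed t(3), skewed exponential). The model is week 8 = rho × baseline + √(1 − rho²) × error + 0.5 × arm. Each setting has 60,000 simulated trials, so the simulation standard error is at most √(0.5 × 0.5 / 60,000) = 0.2 percentage points.

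**Step 1: does the Mann-Whitney variable matter?** Relative to week-8 values alone, the variance of the between-arm contrast is 2(1 − rho) for change and about 1 − rho² for ANCOVA. At rho 0.3 / 0.5 / 0.7 / 0.8 / 0.9 this gives 1.4 / 1.0 / 0.6 / 0.4 / 0.2 for change and 0.91 / 0.75 / 0.51 / 0.36 / 0.19 for ANCOVA.

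Simulated power in %, shown as Mann-Whitney on week 8 / Mann-Whitney on change / ANCOVA:

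| rho | Normal | t(3) | Exponential |
|---|---|---|---|
| 0.3 | 16.1 / 12.9 / 19.0 | 26.0 / 18.5 / 26.0 | 26.1 / 17.7 / 23.0 |
| 0.5 | 16.0 / 16.1 / 22.0 | 25.1 / 24.7 / 30.5 | 23.6 / 23.5 / 26.9 |
| 0.7 | 16.1 / 24.3 / 29.8 | 23.9 / 38.2 / 40.7 | 22.4 / 37.1 / 36.2 |
| 0.8 | 16.0 / 33.9 / 39.7 | 24.2 / 53.7 / 52.5 | 22.5 / 51.4 / 46.7 |
| 0.9 | 16.2 / 60.6 / 65.0 | 25.0 / 81.2 / 75.2 | 24.1 / 77.0 / 69.5 |

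All three methods hold their size under no effect: 4.2 to 5.1% for ANCOVA, 4.2 to 4.5% for Mann-Whitney on change, 4.2 to 4.4% on week-8 values. So the unnamed variable matters, and the direction depends on rho.

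**Step 2: how wide would the missing interval be?** For an unadjusted mean difference the half-width is t(0.975, 18) × √(2/10) = 0.94 SD. Using baseline, the median half-widths with normal data at rho 0.5 / 0.7 / 0.8 / 0.9 are 0.982 / 0.757 / 0.619 / 0.437 SD for the Hodges-Lehmann shift in change and 0.825 / 0.680 / 0.571 / 0.414 SD for ANCOVA. With an assumed 6MWT SD of 80 to 120 m:
- Hodges-Lehmann: 0.437 × 80 = 35 m to 0.982 × 120 = 118 m.
- ANCOVA: 0.414 × 80 = 33 m to 0.825 × 120 = 99 m.

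Most of this range exceeds the cited 22 to 42 m. Dropout widens it: with 8 per arm the Hodges-Lehmann half-width is 1.08 / 0.83 / 0.68 / 0.48 SD.

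**Step 3: what does the signed-rank test show by itself?** These settings illustrate the mechanism and are not predicted error rates.
- Both arms improve equally, by 0.2 / 0.4 / 0.6 / 0.8 / 1.0 SD of change, with no programme effect. The walking arm is significantly improved in 8 / 20 / 38 / 60 / 79% of trials; Mann-Whitney on change is significant in about 4%.
- Controls decline by the same amounts and walkers hold steady. The walking-arm signed-rank test shows improvement in about 2.5%; Mann-Whitney on change is significant in 6 / 12 / 21 / 35 / 52%.

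**The case against.** **A between-arm test is planned, and each test has its own question.** This stands. A reader might infer that the authors mean to treat a significant pre-post change as evidence that the programme works. The documents do not say so: Section 7.0 ties the signed-rank test to change over time and the Mann-Whitney test to the group difference, and Sections 4.0 and 5.1 point to the comparison of arms. The harm in Step 3 needs a misreading that the plan does not state, and no section describes shared improvement in both arms. What remains is that the test sits under the wrong purpose and a label would prevent the misreading.

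**Change scores may already be intended.** They may, since all baseline measures are repeated. A reader might infer that baseline will be ignored; the text supports only that the variable is unnamed. The eight-week home-based trial described in Section 3.3 compared changes from baseline, but that is background and does not bind this plan.

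**Using baseline is not always better.** Correct. At rho 0.3 change scores lose power in all three distributions, and ANCOVA falls below week-8 values with exponential data.

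**A pilot need not estimate effects.** Section 3.5 gives effect estimation as a general reason for pilots, not as an objective of this one, and adds that "pilot studies have little to contribute statistically and theoretically". The sample-size objective chiefly needs SDs, which are planned. The feasibility chart in Attachment 9 was not available to check. This limits the weight of the point, but Section 4.0 does set effect objectives, and an estimate with its interval serves them better than a p-value alone.

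**Conclusion.** The point holds as a minor one. The Mann-Whitney variable is unspecified, no between-arm estimate or interval is planned, and the signed-rank test is listed among comparisons it cannot make. It affects the secondary effect objectives and, to a lesser degree, the sample-size objective. It does not touch the narrative feasibility outcomes.

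ANCOVA has more power than Mann-Whitney on week-8 values at rho 0.5 and above in all three distributions. It also has more than Mann-Whitney on change at rho 0.5 in all three, and falls behind it only at high rho with heavy-tailed or skewed data (from 0.8 with t(3), from 0.7 with exponential). Mann-Whitney on change gains nothing over week-8 values at rho 0.5.

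These comparisons rest on assumed rho, effect and distributions; the metre figures also rest on an assumed SD. A claim that the plan's analysis is invalid, or that baseline adjustment helps whatever the correlation, would go beyond the documents and the figures.

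**What to change.** Amend Section 7.0 for the physical-function tests (6MWT, chair stand, UULEX, handgrip), SF-36 and FACT-L:

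1. Before data are seen, specify one between-arm analysis that uses baseline. Preferably this is ANCOVA of the week-8 value on arm and baseline, reporting the adjusted difference, 95% CI and residual SD. If the rank test is kept, apply Mann-Whitney to change from baseline and report the Hodges-Lehmann shift with its 95% CI.
2. Label the signed-rank results as descriptive within-arm summaries; they may be kept or dropped. Base statements about the effect of NPW only on the between-arm estimate and its interval.

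Cost: wording only, with no extra data or visits. ANCOVA uses one degree of freedom. If rho is as low as 0.3, Mann-Whitney on change gives up power against week-8 values (13% v 16% normal, 19% v 26% t(3), 18% v 26% exponential). There, ANCOVA gains only with normal data (19% v 16%), ties with t(3) (26% each) and loses with exponential data (23% v 26%).
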